2.2 DISPOSITION OF PATIENTS

This section describes patient disposition for both patient study status and the patient analysis populations.

Screened patients are defined as any patient who signed the informed consent.

Randomized patients consist of all screened patients, with a double-blind treatment kit number allocated and recorded in the IVRS/IWRS database, regardless of whether the treatment kit was used or not. Patients treated without being randomized or treated with a double-blind treatment kit

before the randomization will not be considered as randomized and will not be included in any analysis population.

For patient study status in the double-blind period, the total number of patients in each of the following categories will be presented in the clinical study report using a flowchart diagram or summary table:

- Screened patients.
- Screen failure patients and reasons for screen failure.
- Non-randomized but treated patients, if any.
- Randomized patients.
- Randomized but not treated patients and reason for not being treated.
- Randomized and treated patients.
- Patients who completed the double-blind study treatment period as per protocol (as per eCRF end of double-blind treatment form).
- Patients who did not complete the double-blind study treatment period as per protocol (as per eCRF end of double-blind treatment form).
- Patients who discontinued the double-blind study treatment by main reason for permanent treatment discontinuation (as per eCRF end of double-blind treatment form).
- Status at last study contact for patients not entering in the open-label treatment extension.
- Patients participating in the open-label treatment extension period.

For all above categories of patients (except for the screened and non-randomized categories) percentages will be calculated using the number of randomized patients as denominator and summaries will be presented by treatment group as described in Section 2.4.

For patient study status in the open-label period, the total number of patients in each of the following categories will be presented in the clinical study report using a flowchart diagram or summary table:

- Patients treated during the OL period (all patients who received at least one open-label injection during the OL period).
- Patients who completed the OL treatment period as per protocol (as per eCRF end of openlabel treatment form).
- Patients who did not complete the OL treatment period as per protocol (as per eCRF end of open-label treatment form).
- Patients who discontinued OL treatment by main reason for permanent treatment discontinuation.

For patient study status in the open-label period, percentages will be calculated using the number of patients in the OL population (defined in Section 2.3.5) as denominator and summaries will be presented by treatment group as described in Section 2.4.

Reasons for treatment discontinuation will be supplied in tables giving numbers and percentages.

The incidence of premature treatment discontinuation during the double-blind period (irrespective of the reason) and premature treatment discontinuation due to AEs will be presented graphically on randomized and treated patients (as randomized), using Kaplan-Meier method.

Any critical or major protocol deviations (automatic or manual) will be summarized by deviation category in the randomized population for the double-blind period and in the OL population for open-label period. This description will also be performed distinguishing patients with trial impact due to Covid-19 from those who were not (see definition in Section 2.3). In addition, the number (%) of patients by country/site and the listing of patients with at least one critical or major deviation will be provided.

Additionally, the following populations will be summarized:

- Randomized population.
- Efficacy populations: ITT and mITT populations.
- Exploratory efficacy population: FMD sub-study population.
- Safety population.
- Pharmacokinetics population.
- Anti-alirocumab antibody population.
- Open-label population.
- Population without trial impact/disruption due to COVID-19.

Definitions of the study populations are provided in Section 2.3.

2.2.1 Randomization and drug dispensing irregularities

Randomization and drug-dispensing irregularities occur whenever:

1. A randomization is not in accordance with the protocol-defined randomization method, such as a) a patient is randomized based on an incorrect stratum, or b) a patient is randomized twice.

OR

2. A patient is dispensed an IMP kit not allocated by the protocol-defined randomization, such as a) a patient at any time in the study is dispensed a different treatment kit than as randomized (which may or may not contain the correct-as-randomized IMP), or b) a non-randomized patient is treated with IMP reserved for randomized patients.

Randomization and drug-dispensing irregularities will be monitored throughout the study and reviewed on an ongoing basis.

All randomization and drug-dispensing irregularities will be documented in the clinical study report. These irregularities will be summarized on the randomized population. Non-randomized, treated patients will be described separately.

2.3 ANALYSIS POPULATIONS

Patients treated without being randomized will not be considered randomized and will not be included in any analysis population. The safety experience of patients treated and not randomized will be reported separately, and these patients will not be in the safety population.

The randomized population includes any patient who has been allocated to a randomized treatment regardless of whether the treatment kit was used.

For any patient randomized more than once, only the data associated with the first randomization will be used in any analysis population. The safety experience associated with any later randomization will be assessed separately.

2.3.1 Efficacy populations

The primary efficacy analysis population will be the ITT population.

2.3.1.1 Intent-to-treat population

The ITT population is defined as all randomized patients.

Patients in the ITT population will be analyzed according to the treatment group allocated by randomization (ie, as-randomized treatment group).

2.3.1.2 Modified Intent to treat population

The mITT population is defined as all randomized patients who took at least one dose or part of a dose of the double-blind IMP injection.

Patients in the mITT population will be analyzed according to the treatment group allocated by randomization (ie, as-randomized treatment group).

2.3.1.3 FMD sub-study population

The analysis of the FMD will be performed on randomized patients included in the sub-study with a baseline and a post-baseline FMD assessment available. Patients in the FMD sub-study population will be analyzed according to the treatment group allocated by randomization (ie, as-randomized treatment group).

2.3.2 Safety population

The Safety population considered for safety analyses will be the randomized patients who actually received at least one dose or part of a dose of the double-blind IMP injection. Patients will be analyzed according to the treatment actually received (ie, as-treated treatment group).

In addition, randomized patients for whom it is unclear whether they took the study medication will be included in the safety population in the treatment group as randomized.

Within each dosing regimen cohort, for patients receiving mistakenly both placebo and alirocumab (regardless of the dose) IMP injection during the double-blind period (cases reported as protocol deviation), the treatment group used for as-treated analysis will be defined according to the treatment (alirocumab or placebo) of which the patient received highest number of injections. In case of the same number of injections of each treatment is received, the as-treated treatment group will be the as-randomized group. Of note, placebo injections allocated by IVRS/IWRS to maintain the blind for the alirocumab Q4W group ("sham Q2W") will not be taken into account in the derivation of the "as-treated treatment group".

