11.3.2 Safety population

The safety analysis will be performed on the safety population. The safety population consists of the randomized population who did actually receive at least one dose or partial dose of investigational product.

Patients in the safety population will be analyzed according to the treatment actually received.

In addition:

- Nonrandomized but treated patients will not be part of the safety population, but their safety data will be presented separately.
- Randomized patients for whom it is unclear whether they took the study medication will be included in the safety population as randomized.
- For patients receiving more than 1 study treatment during the trial, the treatment group allocation for as-treated analysis will be the one to which the patient was treated with the longest duration.

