Q2W dosing regimen cohort:

The first half of the total patient population (approximately 75 patients) will be randomized to receive Q2W subcutaneous (SC) injections of either alirocumab or placebo, starting at the randomization Visit (Week 0) and continuing up to the end of the double-blind period.

For patients randomized to receive alirocumab the following doses based on BW will be initially administered:

- 40 mg for BW <50 kg or,
- 75 mg for BW \geq 50 kg.

At Week 12 patients randomized to alirocumab will either, in a blinded manner:

- Continue alirocumab 40 mg or 75 mg Q2W, if the Week 8 LDL-C is <110 mg/dL (2.85 mmol/L) OR
- Have a dose up-titration to alirocumab 75 mg Q2W (for patients initially on 40 mg Q2W) or 150 mg Q2W (for patients initially on 75 mg Q2W) if the Week 8 LDL-C is ≥110 mg/dL (2.85 mmol/L).

Q4W dosing regimen cohort:

The second half of the patient population (ie, approximately 75 patients) will be enrolled in a Q4W dosing regimen cohort. During the first 12 weeks of the double-blind period, all patients will receive SC injection(s) Q4W of alirocumab or placebo. After Week 12, with regard to the possible dose-adjustment in some patients and the need for maintaining the double-blind until the end of the double-blind period, all patients will receive SC injection(s) Q2W.

For patients randomized to alirocumab the following doses based on BW will be initially administered:

- 150 mg Q4W for BW <50 kg or,
- $300 \text{ mg } \text{Q4W for BW} \ge 50 \text{ kg.}$

At Week 12, patients randomized to alirocumab will either, in a blinded manner:

• Continue alirocumab 150 mg or 300 mg Q4W, if the Week 8 LDL-C is <110 mg/dL (2.85 mmol/L) alternating with Q4W placebo injection ("sham" Q2W regimen) OR

• Have a dose adjustment to 75 mg Q2W (for patients on 150 mg Q4W) or 150 mg Q2W (for patients on 300 mg Q4W) if the Week 8 LDL-C is ≥110 mg/dL (2.85 mmol/L) ("actual" Q2W regimen).

Note: participants enrolled in the placebo Q4W group will receive injection of placebo of alirocumab Q4W for the first 12 weeks, then injection of placebo of alirocumab Q2W until the end of the double-blind period.

Open-label treatment period

The open-label (OL) treatment period consists of 80 weeks of open-label alirocumab SC Q2W or Q4W depending on the frequency of the dosing regimen initiated at randomization.

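### SAP 2.3.2 places patients given both treatments in a safety arm by injection count where the protocol uses duration, and in the Q4W cohort the two rules can give opposite labels

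*SAP*

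**What the plan says.** Protocol 11.3.2 covers patients who received more than one study treatment: "the treatment group allocation for as-treated analysis will be the one to which the patient was treated with the longest duration". It gives no rule for equal durations.

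SAP 2.3.2 covers patients who by mistake received both alirocumab and placebo in the double-blind period, within a dosing cohort. Their group is "defined according to the treatment (alirocumab or placebo) of which the patient received highest number of injections". It adds a tie-break: "In case of the same number of injections of each treatment is received, the as-treated treatment group will be the as-randomized group". It also leaves out of the count the "placebo injections allocated by IVRS/IWRS to maintain the blind for the alirocumab Q4W group", which it labels the sham Q2W regimen.

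The Q4W cohort does not have a constant injection interval. SAP 1.1 states: "During the first 12 weeks of the double-blind period, all patients will receive SC injection(s) Q4W of alirocumab or placebo". For placebo patients after Week 12 it continues: "then injection of placebo of alirocumab Q2W until the end of the double-blind period". Alirocumab patients without dose adjustment stay on active drug every 4 weeks, with placebo in the alternate slots. Dose-adjusted patients receive active drug every 2 weeks, and those of 50 kg or more also get a placebo syringe alongside each active one (Protocol 8.1).

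**The concern.** Two governing documents give different derivations of the same variable. Where the injection interval is constant this hardly matters, because the count is proportional to time. In the Q4W cohort a post-Week 12 placebo injection covers half the time of an earlier injection but carries the same weight. The SAP recognises the difference elsewhere: its exposure formula (2.4.3.1) adds 28 days after the last injection for patients who stopped before the Week 12 switch, and 14 days otherwise. Its as-treated rule does not.

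The consequence of most interest is a patient with more time on alirocumab than on placebo whose adverse events are reported under placebo. Protocol 9.2.4.1 says residual alirocumab effect is possible until 10 weeks after treatment stops. With a last active dose at Week 8, that reaches Week 18 of the 24-week period. Safety was the stated reason for raising the sample from 90 to 150 (Protocol 11.1).

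**Working it through.** The documents state no figure to reproduce. The check applies both rules to the schedule.

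**Inputs**
- Q4W cohort, Weeks 0-12: every 4 weeks, so Weeks 0, 4, 8 = 3 administrations (SAP 1.1, Protocol 8.1).
- Q4W cohort on placebo, Weeks 12-24: every 2 weeks, so Weeks 12, 14, 16, 18, 20, 22 = 6 administrations.
- Time covered: 28 days per administration in the first phase (3 × 28 = 84 days) and 14 days per placebo administration in the second.
- The administration weeks are derived from the stated frequencies, assuming full adherence until the patient stops.

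**Placebo-randomised patient, alirocumab in error in Weeks 0-12, then k placebo administrations, then stop**

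| k | Count, alirocumab v placebo | SAP label | Weeks, alirocumab v placebo | Protocol label |
|---|---|---|---|---|
| 1 | 3 v 1 | alirocumab | 12 v 2 | alirocumab |
| 2 | 3 v 2 | alirocumab | 12 v 4 | alirocumab |
| 3 | 3 v 3 | tie, as randomised: placebo | 12 v 6 | alirocumab |
| 4 | 3 v 4 | placebo | 12 v 8 | alirocumab |
| 5 | 3 v 5 | placebo | 12 v 10 | alirocumab |
| 6 | 3 v 6 | placebo | 12 v 12 | tie, no rule given |

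The counts themselves point opposite ways at k = 4 and 5. At k = 3 the labels also differ, through the SAP tie-break. For patients of 50 kg or more, two syringes per administration double both sides (for example 6 v 8), and the label does not change.

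**Alirocumab-randomised patient, no dose adjustment, placebo in error after Week 12.** If all six placebo administrations count, it is 3 v 6: placebo. If placebo falling in the three sham slots is left out, it is 3 v 3: a tie, so alirocumab. The exclusion covers placebo allocated by the system to keep the blind; whether placebo given in error in those slots qualifies is not stated.

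**Reverse order, a full 12 + 12 weeks**
- Placebo, then unadjusted alirocumab, sham not counted: 3 v 3, as randomised.
- Placebo, then dose-adjusted alirocumab, under 50 kg: 6 alirocumab v 3 placebo, alirocumab.
- The same at 50 kg or more, counting syringes: 6 alirocumab v 6 placebo if the companion syringe is ignored, as randomised. By administrations it is 6 v 3, alirocumab. The SAP wording does not settle which unit applies.

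**Q2W cohort.** A 12 + 12 week mix is 6 v 6 by count and 12 v 12 by time. The rules agree, apart from the protocol's missing tie-break.

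**Size of one reclassification**, using the planned 25 placebo patients per cohort (Protocol 11.1). Suppose x of the other 24 have the event and the mis-dosed patient also has it. Keeping that patient in placebo changes the rate by (x+1)/25 − x/24 = (24 − x)/600. For x = 0 this is 4.0 points; for x = 12 it is 2.0 points. In the pooled placebo column of 50 the maximum is 1/50 = 2.0 points. A mis-dosed patient without the event lowers the placebo rate instead, when x is above zero.

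**The case against.** The case for leaving this alone has real substance.

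- A reader might infer that any patient with 12 weeks of each treatment is put in placebo against the protocol. The documents do not support that. Equal durations are a tie under Protocol 11.3.2, which has no tie-break, so the protocol does not place that patient in alirocumab either. The count gives placebo outright only when alirocumab comes first, and for an unadjusted alirocumab-randomised patient only on one reading of the sham exclusion.
- A reader might infer that the rule hides an alirocumab safety signal. Safety analyses are descriptive. All dispensing irregularities are to be documented in the study report (SAP 2.2.1), and patients with critical or major deviations are listed (SAP 2.2). The distortion is also not one-directional: placebo in Weeks 0-12 followed by 4 or 5 dose-adjusted alirocumab administrations, under 50 kg, is alirocumab by count and placebo by duration.
- A reader might take the silence of SAP 1.5 and 1.6 as an undisclosed change. Both are limited to major changes: 1.5 to protocol amendments, 1.6 to SAP version 2 against version 1. Their silence proves little.
- Kits are dispensed at Weeks 0 and 12, which makes a wrong 12-week supply conceivable. But kits are individually numbered and centrally allocated, and nothing says one kit holds 12 weeks. How often such an error would occur is conjecture.
- Any rule giving a mixed patient one label misattributes some events.

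All of this stands and limits the point. None of it removes the mismatch between the documents or the patients at k = 3 to 5, whose labels differ.

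**Conclusion.** The point holds in limited form. The SAP's count rule departs from the protocol's duration rule, the SAP gives no reason, and in the Q4W cohort the two can disagree because the interval halves at Week 12. The clear case is a placebo-randomised patient with 12 weeks of alirocumab in error followed by 8 to 10 weeks of placebo. With a full 12 weeks of placebo, the SAP gives placebo and the protocol gives no answer.

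The effect is confined to mis-dosed patients, whose number is unknown and may be zero. Each can move a cohort placebo event rate by at most about 4 points, and a pooled rate by about 2. The ITT efficacy analyses use the randomised group and are unaffected. These figures assume the planned group sizes and full adherence up to stopping. This is an alignment worth making because it is nearly free and removes a route by which alirocumab exposure is reported as placebo. It is not a threat to the trial's conclusions.

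**What to change.** In SAP 2.3.2:

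1. Assign by longest duration, as in the protocol, counting administrations and not syringes.
2. Build duration by extending the SAP's 28/14-day exposure convention to every administration: 28 days for each one in Weeks 0-12 of the Q4W cohort, active or placebo, and for each active Q4W administration under the sham regimen; 14 days for every other Q2W administration.
3. Keep ties as randomised, which also supplies what the protocol lacks.
4. State that blind-keeping placebo is never counted, naming both the sham slots and the companion syringe of dose-adjusted patients of 50 kg or more. For the unadjusted alirocumab-randomised patient above, duration gives 84 v 84 days (tie, alirocumab) or, with sham slots left out, 84 v 42, so the label no longer depends on the reading.
5. List every patient with at least one alirocumab injection who is analysed as placebo. This matters because a placebo-randomised patient with 12 + 12 weeks remains a tie and stays in placebo.

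The cost is a few sentences, one derivation and one listing. If the sponsor prefers counts, the SAP should record the departure from the protocol and justify it.

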2.3.3 Anti-alirocumab antibody population

The ADA analysis will be performed on all randomized and treated patients (safety population) with an available ADA sample at Week 0 (baseline) and at least one non-missing ADA sample post first double-blind IMP injection and up to Week 24/early termination or up to first open-label IMP injection for patient proceeding into open-label period.

2.3.4 Pharmacokinetics population

The PK analysis will be performed on all randomized and treated patients (safety population) with at least one non-missing drug concentration value (including BLQ values) post first double-blind IMP injection and up to Week 24/early termination visit or up to first injection in the open-label period, for patients proceeding into the open-label period.

2.3.5 Open-label population

The OL population considered for all analyses in the OL treatment period will be all randomized patients who received at least one dose or part of dose of IMP during the OL treatment period.

2.3.6 Population without trial impact/disruption due to COVID-19

The population without trial impact/disruption due to COVID-19 will be defined as any patient without any of the following:

- Major or critical deviation related to COVID-19
- Permanent treatment discontinuation related to COVID-19
- Permanent study discontinuation related to COVID-19.
2.4 STATISTICAL METHODS

General rules

Analyses will be performed separately for the double-blind and the OL periods, unless otherwise noted.

Double-blind period

Unless otherwise specified, the analyses will be performed by treatment group (placebo, alirocumab) within each dosing regimen cohort.

In addition, for disposition, populations, demographic/baseline characteristics, safety and other endpoints (refer to Section 2.1.5), analyses will be provided by treatment group (placebo, alirocumab) regardless of the dosing regimen cohorts (pooled across cohorts).

Of note, an Overall column will be displayed for populations, demographics and baseline characteristics.

OL period

The summaries will be displayed according to the treatment group (placebo, alirocumab) received in the double-blind period and Overall within each dosing regimen cohort (dosing regimen initiated at the randomization).

For disposition, populations, demographic/baseline characteristics, safety and other endpoints, analyses will be also provided by treatment group received in the double-blind period regardless of the dosing regimen cohorts, and Overall.

2.4.1 Demographics and baseline characteristics

Parameters described in Section 2.1.1 will be summarized using descriptive statistics.

Continuous data will be summarized using the number of available data, mean, SD, median, minimum and maximum for each treatment group. First quartile (Q1) and third quartile (Q3) will be also provided for baseline lipid parameters and HbA_{1c}. Categorical and ordinal data will be summarized using the number and percentage of patients.

Parameters will be summarized on the randomized population analyzed in the as-randomized treatment group. Similar analyses will be done on safety population in the as-treated treatment group and will be included in the appendices if the size of the safety population is different (>10%) from the size of the randomized population for any dosing regimen/treatment group. In the randomized population, parameters will also be summarized within each randomization stratum as per IVRS/IWRS.

All reported patient's medical and surgical history will be presented by primary SOC and HLT. The tables will be sorted by SOC internationally agreed order and decreasing frequency of HLT based on the overall incidence across treatment groups. In addition, all medical history of specific interest (see Section 2.1.1) will be summarized.

These parameters will be also summarized in the OL population.

P-values on demographic and baseline characteristic data will not be calculated.

No specific description of safety parameters will be provided at baseline. If relevant, the baseline values will be described along with each safety analysis.

